7.1 Adverse Event Monitoring

Adverse event data collection and reporting, which are required as part of every clinical trial, are done to ensure the safety of subjects enrolled in the studies as well as those who will enroll in future studies using similar agents. Adverse events are reported in a routine manner at scheduled times during a trial. Additionally, certain adverse events must be reported in an expedited manner to allow for optimal monitoring of patient safety and care.

As far as possible, each adverse event should be evaluated to determine:

- duration (start and end dates)
- severity (grade)
- seriousness
- relationship to study agent
- action taken (i.e., none, study agent modification, medical intervention)
- outcome (i.e., resolved without sequelae, resolved with sequelae, ongoing)

Adverse events monitoring begins at the time of initiating study treatment through **90** days following the last administration of study treatment or study discontinuation/termination, or the initiation of new anti-cancer therapy, whichever is earlier, whether or not related to avelumab.

Note: Serious adverse events must be recorded in the case report forms for this 90 day-period; however, non-serious adverse events need only be recorded through 28 days post last study drug administration.

All patients experiencing an adverse event at least possibly related to study treatment will be monitored until:

- the adverse event resolves or the symptoms or signs that constitute the adverse event return to baseline;
- > any clinically significant abnormal laboratory values have returned to baseline;
- there is a satisfactory explanation other than the study drug for the changes observed; or
- ➤ death.

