2.3 Endpoints

Primary Endpoint:

1. Overall response rate (defined as complete or partial response) at 6 months based on RECIST.

Secondary Endpoints:

- 1. Duration of response, defined as time from documentation of tumor response to disease progression
- 2. Progression-free survival, defined as the time start of Avelumab until disease progression or death
- 3. Overall survival, defined as the time from start of Avelumab to death from any cause

- 4. Toxicity (grade 3 or higher), as defined by CTCAE 4.03.
- 5. Exploratory correlatives:
 - Tissue (new biopsy required upon study entry prior to therapy; repeat biopsy at time of progression will be encouraged but optional):
 - PDL1 expression by immunohistochemistry (ABC technique [Vector labs], using rabbit mAb 1:200 [Cell Signaling])
 - Immunophenotyping by flow cytometry:
 - T cell subsets (CD4, CD8, FOXP3)
 - Macrophages (CD68)
 - Cytokeratin 5/6 (by immunohistochemistry)
 - Peripheral blood (comparison of baseline and 12 week post-treatment samples, unless otherwise denoted)
 - TCR and BCR sequencing
 - T cell subsets (CD3, CD4, CD8, CD25, FOXP3)
 - B cells (CD19, CD20)
 - Macrophage I/II and myeloid-derived suppressor cells (MDSC) (CD16, CD68, CD206)
 - Natural killer cell activity (CD56, CD16)
 - EBV DNA plasma levels (will be performed at baseline, every 12 weeks after treatment initiation and at end of treatment)
- 6. Clinical activity of Avelumab as defined by overall response rate will also be measured utilizing immune-related RECIST.

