4.3 Toxicities and Dosing Delays/Dose Modifications

Any patient who receives treatment on this protocol will be evaluable for toxicity. Each patient will be assessed for the development of toxicity according to the NCI Common Toxicity Criteria for Adverse Events (CTCAE), version 4.03.

Adverse events (both non-serious and serious) associated with avelumab exposure may represent an immunologic etiology. These adverse events may occur shortly after the first dose or several months after the last dose of treatment. Avelumab must be withheld for drug-related toxicities and severe or life-threatening AEs as listed in Sections 4.3.1-4.3.3.

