Grade 3 to 4	Delay or discontinue avelumab	If improves to Grade 1:
Covering > 30% body surface area;	therapy	Taper steroids over at least 1 month
Life-threatening consequences		and add
	Consider skin biopsy	prophylactic antibiotics for
		opportunistic
	Dermatology consult	infections
		Resume avelumab therapy
	1.0 to 2.0 mg/kg/day	
	methylprednisolone i.v. or i.v.	
	equivalent	

Pulmonary irAEs		
Grade of Pneumonitis	Management	Follow-up
(NCI-CTCAE v4)		De images at least average 2 verales
Grade 1 Radiographic changes only	Consider delay of avelumab therapy Monitor for symptoms every 2 to 3 days	Re-image at least every 3 weeks If worsens: Treat as Grade 2 or Grade 3 to 4
	Consider Pulmonary and Infectious Disease consults	
Grade 2	Delay avelumab therapy	Re-image every 1 to 3 days
Mild to moderate new symptoms	Pulmonary and Infectious Disease consults	If improves: When symptoms return to near
	Monitor symptoms daily; consider hospitalization	baseline, trapper steroids over at least 1 month and then resume avelumab therapy and consider
	1.0 mg/kg/day methyl-prednisolone i.v. or oral equivalent	prophylactic antibiotics If not improving after 2 weeks or worsening: Treat as Grade 3 to 4
	Consider bronchoscopy, lung biopsy	
Grade 3 to 4	Discontinue avelumab therapy	If improves to Baseline:
Severe new symptoms; New/worsening hypoxia; Life-	Hospitalize	Taper steroids over at least 6 weeks
threatening	Pulmonary and Infectious Disease consults	If not improving after 48 hours or worsening: Add additional immunosuppression (for example, infliximab,
	2 to 4 mg/kg/day methylprednisolone i.v. or i.v. equivalent	cyclophosphamide, i.v. immunoglobulin, or mycophenolate mofetil)
	Add prophylactic antibiotics for opportunistic infections	
	Consider bronchoscopy, lung biopsy	
Hepatic irAEs		
Grade of Liver Test Elevation (NCI-CTCAE v4)	Management	Follow-up
Grade 1	Continue avelumab therapy	Continue liver function monitoring
Grade 1 AST or ALT > ULN to 3.0 x ULN and/or Total bilirubin > ULN to 1.5 x ULN		If worsens: Treat as Grade 2 or 3-4
Grade 2	Delay avelumab therapy	If returns to Baseline:
AST or ALT > 3.0 to \leq 5 x ULN and/or total bilirubin > 1.5 to \leq 3 x ULN	Increase frequency of monitoring to every 3 days	Resume routine monitoring, resume avelumab therapy
		If elevations persist > 5-7 days or
		worsen : 0.5 to 1 mg/kg/day
		methylprednisolone or oral
		equivalent and when LFT returns to Grade 1 or Baseline, taper steroids
		over at least 1 month, consider

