4.9 End of Study Treatment and Follow Up

After the last dose of study treatment, each patient will be followed for 28 days for adverse event monitoring (serious adverse events will be collected for 90 days after the end of treatment as described in Section 7.1). Patients removed from treatment for unacceptable adverse events will be followed until resolution or stabilization of the adverse event.

Patients who discontinue for reasons other than progressive disease will have post-treatment follow-up approximately every 3 months for disease status until disease progression, initiation of a non-study cancer treatment, withdrawal of consent or lost to follow-up.

After documented disease progression, each patient will be followed approximately every 3-6 months by review of medical records, telephone, or review of the Social Security Index for overall survival until death, withdrawal of consent, or the end of the study, whichever occurs first.

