5.4 Follow-up Procedures

Patients discontinuing study treatment will be followed every three months after the last dose of study treatment until death with:

- Tumor assessments if they discontinued from study treatment without disease progression- until disease progression or initiation of a new anti-cancer therapy, and
- Survival contacts via medical record review, telephone call, or review of the Social Security Index.

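### New non-serious grade 3+ events need not be recorded after day 28, and no scheduled contact asks about SAEs from then to day 90, so late toxicity may be undercounted

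*Combined protocol and SAP*

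**What the plan says.** On timing of risk, Section 4.3 says of adverse events that may be immune in origin: "These adverse events may occur shortly after the first dose or several months after the last dose of treatment".

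On what is to be measured, Section 2.3 lists as secondary endpoint 4 "Toxicity (grade 3 or higher), as defined by CTCAE 4.03". Neither that entry nor the safety analysis in Section 9.5 sets a time window or limits the endpoint to serious events.

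On recording, the Note in Section 7.1 splits events by seriousness. For serious events, "Serious adverse events must be recorded in the case report forms for this 90 day-period". For the rest, "non-serious adverse events need only be recorded through 28 days post last study drug administration". The 90-day period ends sooner if new anti-cancer treatment starts: "or the initiation of new anti-cancer therapy, whichever is earlier, whether or not related to avelumab". Section 4.9 repeats the 28/90-day split and refers to Section 7.1 for the serious events.

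On enquiry, the Schedule of Events and Section 5.3.6 place the last adverse event assessment at End of Treatment, 28 days (± 7) after the last dose. The Schedule's adverse event row is blank under Follow-up. Section 5.4 sets contacts every three months. Patients who stopped without progression have tumor assessments, and all patients have "Survival contacts via medical record review, telephone call, or review of the Social Security Index". After progression, Section 4.9 says "each patient will be followed approximately every 3-6 months by review of medical records, telephone, or review of the Social Security Index". Section 5.0 states that safety will be monitored in the follow-up period too, and refers to the Schedule for procedures.

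**The concern.** The endpoint, the stated risk period and the recording rule do not match. A new grade 3 event that does not meet a seriousness criterion and begins on day 40 satisfies the endpoint as written, falls within the delay that Section 4.3 describes, and need not be recorded. Section 4.3.1 shows that such events are plausible: it groups AST or ALT above 5 x ULN as grade 3 to 4, and Section 7.3 does not make a grade 3 event serious by grade alone.

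Serious events raise a different problem. The duty to record them runs to day 90, but no listed procedure asks the patient about them after End of Treatment. Whether one enters the data then depends on the site happening to hear of it.

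At stake is a secondary, descriptive safety result in a single-arm trial of 39 patients. Any event lost this way lowers the reported toxicity rate, and the annual summaries to the DSMB (Section 10.6) would carry the same omission.

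**Working it through.** **1. Days without a scheduled enquiry.** Inputs: SAE window of 90 days (Section 7.1); End of Treatment at day 28 ± 7, so day 21 to day 35 (Schedule, Section 5.3.6).

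- Latest visit: 90 − 35 = 55 days; 55/90 = 61%.
- Earliest visit: 90 − 21 = 69 days; 69/90 = 77%.
- The first three-monthly contact falls at about 365.25/4 = 91 days, just after the window closes, and an adverse event enquiry is not among its listed contents.

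**2. Days on which a new non-serious event need not be recorded although SAEs must be.** Days 29 to 90: 90 − 28 = 62 days. If the End of Treatment visit takes place on day 21, the last enquiry also comes 7 days before the day-28 cut-off.

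**3. The plan's reference rate.** Section 1.6 gives grade ≥ 3 treatment-related events in 77 subjects (10.7%) of the pooled expansion cohort of 717. 77/717 = 0.1074, so the figure reproduces.

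**4. Expected number in this trial.** 39 × 0.1074 = 4.19, about 4 patients with a grade 3+ related event.

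**5. Possible loss.** Let f be the share of those patients whose event is non-serious and begins after day 28. The documents do not give f; the range 0% to 30% is an assumption. Expected number missed = 4.19 × f; recorded rate = 10.74% × (1 − f).

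| f | Patients missed of 39 | Recorded rate |
|---|---|---|
| 0% | 0 | 10.7% |
| 5% | 0.2 | 10.2% |
| 10% | 0.4 | 9.7% |
| 20% | 0.8 | 8.6% |
| 30% | 1.3 | 7.5% |

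**6. Scale.** The exact 95% CI for 4/39 (10.3%) is 2.9% to 24.2%. Even the largest loss in the table, 10.7 − 7.5 = 3.2 percentage points, is small beside it.

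Two limits apply. The 10.7% counts treatment-related events only, whereas endpoint 4 is not so restricted. And the table covers only the recording rule for non-serious events; the documents give nothing from which to estimate serious events missed through passive ascertainment.

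**The case against.** The strongest reply is that the plan already protects against much of this.

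- **Serious events are in scope to day 90.** They must be recorded (Section 7.1) and reported within 24 hours of learning of them (Section 7.6.2). This stands: collection is not absent. But a duty that begins on learning of an event does not produce the knowledge, so ascertainment after End of Treatment remains passive.
- **Known events are followed up.** Section 4.9 follows patients removed for unacceptable adverse events until resolution or stabilization, and Section 7.1 monitors every at least possibly related event until it resolves or is otherwise accounted for. This stands and narrows the point to new events. Because grade 3 to 4 pneumonitis carries the instruction "Taper steroids over at least 6 weeks", a reader might infer that flares during a taper go unrecorded. A flare of an unresolved event is covered by these rules; a new non-serious event, such as an infection during the taper, is not.
- **Other routes exist.** An investigator may judge an event medically important and hence serious (Section 7.3), and Section 7.6.3 requires notification of non-serious events of clinical interest with no day limit. The first is discretionary and the second is not defined, so neither closes the gap.
- **Section 5.0 promises safety monitoring in follow-up.** It does, but neither the Schedule nor Section 5.4 lists a procedure for it.

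Three stronger readings are tempting and are not supported. One is that Section 4.9 contradicts Section 7.1 by omitting the cut at new therapy; Section 4.9 refers to Section 7.1 for SAE collection, so it takes over that window. Ending collection at new anti-cancer therapy is a debatable but explicit choice, repeated in Section 7.6.1. Another is that follow-up is for survival only; patients without progression also have tumor assessments. The third is that 55 to 69 days of data are lost; those are days without a scheduled question, and one look-back enquiry can cover them.

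**Conclusion.** The point holds in a limited form. The day-28 rule lets new non-serious grade 3+ events go unrecorded although the endpoint has no such limit and Section 4.3 expects delayed events. Serious events from End of Treatment to day 90 must be recorded but are not actively sought. Late grade 3+ and immune-related events may therefore be undercounted.

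A reader might conclude that they are undercounted, or that the bias is material. The documents do not show that, because they give no late-event rate. Under the assumed share of 0% to 30%, with the 10.7% rate carried over from the earlier avelumab trial, the loss is 0 to 1.3 of 39 patients. No test or decision rule depends on this endpoint, and the primary response analysis is unaffected. The change is worth making because the mismatch is plain in the text and costs little to remove.

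**What to change.** (a) In the Follow-up column of the Schedule and in Section 5.4, add one adverse event enquiry at about 90 days after the last dose for every patient, progressed or not, by telephone or visit, combined with the first three-month contact. Record review or a Social Security Index look-up alone should not count. This also gives the Section 5.0 commitment a procedure.

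(b) In the Section 7.1 Note, require all grade 3+ and all suspected immune-related events, serious or not, to be recorded over the same window as SAEs. State that window for the grade 3+ endpoint in Sections 2.3 and 9.5, and bring the 28-day wording in Section 4.9 into line. A 90-day window still falls short of several months, so the report should name the window next to the rate.

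Cost: protocol wording, one Schedule entry and about 39 short contacts near a date already planned. Some late events will have uncertain attribution, and the reported toxicity rate may be slightly higher.

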7.2 Severity

All adverse events will be graded according to the NCI Common Terminology Criteria for Adverse Events (CTCAE) version 4.03. The CTCAE v4.03 is available at http://ctep.cancer.gov/reporting/ctc.html

If no CTCAE grading is available, the severity of an AE is graded as follows:

Mild (grade 1): the event causes discomfort without disruption of normal daily activities; intervention not indicated.

Moderate (grade 2): the event causes discomfort that affects normal daily activities; minimal, local or noninvasive intervention indicated.

Severe (grade 3): the event makes the patient unable to perform normal daily activities or significantly affects his/her clinical status; intervention indicated.

Life-threatening (grade 4): the patient was at risk of death at the time of the event; urgent intervention indicated.

Fatal (grade 5): the event caused death.

7.3 Seriousness

A "serious" adverse event is defined in regulatory terminology as any untoward medical occurrence that:

1. Results in death.

If death results from (progression of) the disease, the disease should be reported as event (SAE) itself.

2. Is life-threatening.

(the patient was at risk of death at the time of the event; it does not refer to an event that hypothetically might have caused death if it were more severe).

- 3. **Requires in-patient hospitalization or prolongation of existing hospitalization**. Note: Hospitalization (including hospitalization for an elective procedure) for a preexisting condition which has not worsened does not constitute a serious adverse event.
- 4. **Results in persistent or significant disability or incapacity**. Substantial disruption of one's ability to conduct normal life functions.
- 5. Is a congenital anomaly/birth defect.
- 6. Is an important medical event.

Any event that does not meet the above criteria, but that in the judgment of the investigator jeopardizes the patient, may be considered for reporting as a serious adverse event. The event may require medical or surgical intervention to prevent one of the outcomes listed in the definition of "Serious Adverse Event".

For example: allergic bronchospasm requiring intensive treatment in an emergency room or at home; convulsions that may not result in hospitalization; development of drug abuse or drug dependency.

7.4 Relationship

Attribution categories for adverse events in relationship to protocol therapy are as follows:

Definite – The AE is clearly related to the study treatment.

Probable – The AE is likely related to the study treatment.

Possible – The AE may be related to the study treatment.

Unlikely – The AE is doubtfully related to the study treatment.

Unrelated – The AE is clearly NOT related to the study treatment.

7.5 **Prior experience**

Expected events are those that have been previously identified as resulting from administration of the agent. An adverse event is considered unexpected, for expedited reporting purposes only, when either the type of event or the severity of the event is not listed in the current known adverse events listed in the agent clinical experience section of this protocol or the current Investigator's Brochure (or Product Label when applicable).

7.6 Reporting Requirements for Adverse Events

7.6.1 Expedited Reporting

Serious adverse events, or a follow up to a serious adverse event, including death due to any cause other than progression of the cancer under study that occurs to any subject from the time study treatment initiation through 90 days following cessation of treatment, or the initiation of new anti-cancer therapy, requires expedited reporting as described below.

7.6.2 Expedited Reporting to Site Principal Investigator and Study Chair

The Study Chair and Site Principal Investigator must be notified within 24 hours of learning of any serious adverse events (SAEs).

7.6.3 Expedited Reporting to Pfizer

Pfizer must be notified within 2 working days of learning of any SAEs or non-serious Events of Clinical Interest:

> Name: TBD Attn: TBD FAX: TBD

The Study Chair will submit a copy of all 15 Day FDA Reports to Pfizer at the time of submission to FDA.

7.6.4 Expedited Reporting to Regulatory Authorities

- A. The Institutional Review Board (IRB) of each site must be notified by the site principal investigator according to their local policies.
- B. The UCSD Human Research Protections Program (HRPP) and Moores Cancer Center Data and Safety Monitoring Board (DSMB) must be notified within 10 business days of "any unanticipated problems involving risk to subjects or others" (UPR).

The following events meet the definition of UPR:

- 1. Any serious event (injuries, side effects, deaths or other problems), which in the opinion of the Principal Investigator was unanticipated, involved risk to subjects or others, and was possibly related to the research procedures.
- 2. Any serious accidental or unintentional change to the IRB-approved protocol that alters the level of risk.
- 3. Any deviation from the protocol taken without prior IRB review to eliminate apparent immediate hazard to a research subject.
- 4. Any new information (e.g., publication, safety monitoring report, updated sponsor safety report), interim result or other finding that indicates an unexpected change to the risk/benefit ratio for the research.
- 5. Any breach in confidentiality that may involve risk to the subject or others.
- 6. Any complaint of a subject that indicates an unanticipated risk or that cannot be resolved by the Principal Investigator.
- **C.** The FDA must be notified by the Study Chair according to the following timelines:
 - within 7 calendar days of any unexpected fatal or life-threatening adverse event with possible relationship to study drug, and
 - within 15 calendar days of any event that is considered: 1) serious, 2) unexpected, and 3) at least possibly related to study participation.

7.6.5 Routine Reporting Requirements for Adverse events

A. The **IRB of each site** must be notified by the site principal investigator according to their local policies.

- **B.** The **UCSD HRPP** must be notified of any adverse events that are not unanticipated problems involving risk to subjects or others (non-UPRs) at the time of the annual Continuing Review.
- **C.** The **FDA** must be notified by the Study Chair of all non-serious adverse events annually at the time of the annual report.

8.0 AGENT INFORMATION

8.1 Avelumab

Please refer to the Product Label and Investigator's Brochure for more comprehensive information.

Other names for the drug: MSB0010718C

Mechanism of action (or Product description):

Avelumab binds PD-L1 and blocks the interaction between PD-L1 and PD-1. This removes the suppressive effects of PD-L1 on anti-tumor CD8+ T cells, resulting in the restoration of cytotoxic T cell response.

Availability: Clinical supplies are provided by Pfizer, and will be affixed with a clinical label in accordance with regulatory requirements.

Dosage Forms and Strengths:

Avelumab drug product is a sterile, clear, and colorless concentrate for solution presented at concentrations of 10 mg/mL and 20 mg/mL in European Pharmacopeia (Ph. Eur.) and United States Pharmacopeia (USP) type I glass vials closed with a rubber stopper and sealed with an aluminum Flip Off® crimp seal closure.

Each single-use 10 mg/mL vial contains 80 mg of avelumab as a preservative-free acetatebuffered solution (pH 5.5) containing Mannitol, Methionine, and Polysorbate 20 (Tween 20).

Each single-use 20 mg/mL vial contains 200 mg of avelumab as a preservative-free acetate-buffered solution (pH 5.2) containing Mannitol, and Polysorbate 20 (Tween 20).

Preparation:

Avelumab will be prepared according to the product label unless otherwise directed in the Pharmacy Manual.

Avelumab drug product must be diluted with 0.45% or 0.9% saline solution (sodium chloride injection) supplied in an infusion bag. Detailed information on infusion bags and medical devices to be used for the preparation of the dilutions and subsequent administration will be provided in the manual of preparation.

To prepare the dilutions, subsequent preparation steps must be accomplished by adequate trained personnel under a laminar flow box using aseptic techniques:

Prior to the preparation of the dilution for final infusion, allow each vial to equilibrate to room temperature. Use a disposable syringe equipped with a needle of suitable size to remove a volume of sodium chloride solution to be replaced by avelumab from the infusion bag and discard the removed solution. Use a new disposable syringe equipped with a needle of suitable size to inject a volume of avelumab drug product identical to the discarded volume of sodium

chloride solution into the infusion bag. Gently invert the mixture 10 times. Infusion bags must not be shaken, in order to avoid foaming or excessive shearing of the protein solution. The preparation must be carefully inspected as it should result in a homogeneous looking clear solution, free of visible particles.

For detailed information on the assigned dose levels and the concrete volumes to be replaced to prepare the target doses, please refer to the clinical trial protocol or to the manual of preparation.

Storage and stability:

Avelumab drug product must be stored at 2°C to 8°C until use. The storage condition is based on data from ongoing long term stability studies with avelumab.

Avelumab drug product stored at room (23°C to 27°C) or higher temperatures for extended periods of time might be subject to degradation. Avelumab drug product must not be frozen. Rough shaking of the solution must be avoided.

For application in clinical trials, avelumab drug product must be diluted with 0.45% or 0.9% saline solution (sodium chloride injection) supplied in an infusion bag. The chemical and physical in-use stability for the infusion solution of avelumab in 0.45% or 0.9% saline solution has been demonstrated for a total of 24 hours at room temperature. However, from a microbiological point of view, the diluted solution should be used immediately and is not intended to be stored unless dilution has taken place in controlled and validated aseptic conditions. If not used immediately, in-use storage times and conditions prior to administration are the responsibility of the user.

No other drugs should be added to the solution for infusion containing avelumab.

Route of administration for this study: Intravenous infusion over 1 hour.

Side effects:

For the purpose of regulatory reporting requirements during clinical development, the following AEs will be considered as expected and met the threshold of casual association (based on comprehensive evaluation) defined by the Sponsor:

- Infusion-related reactions including hypersensitivity reactions
- Immune-mediated adverse reactions like immune-mediated colitis, immune-mediated hepatitis including autoimmune hepatitis, immune-mediated thyroid disorders including hyperthyroidism, hypothyroidism, thyroiditis and autoimmune thyroiditis, immunemediated pneumonitis, immune-mediated skin reactions including rash, pruritis, rash generalized, rash macula-papular, erythema, pemphigoid, other immune mediated reactions including myocarditis, adrenal insufficiency, uveitis, iritis, myositis.

